4.2 Study design

The study hypothesis will be tested using a cohort study design, applying mixed methods (quantitative and qualitative research) to assess clinical and economic indicators, implementation, and patient experience.

4.3 Pharmacy recruitment

This state-wide study and as part of the contract with the NSW Government, the researchers are obliged to include any approved pharmacy and approved pharmacist in NSW that request participation. Furthermore, as part of the Contract with NSW Health, we have agreed to include 5 pharmacies in the ACT.

In the first instance, the NSW Ministry of Health created an expression of interest (EOI) form on their website (https://www.health.nsw.gov.au/pharmaceutical/Pages/community-pharmacy-pilot.aspx) to which pharmacies were encouraged to complete if interested in participating. Similarly, the Pharmacy Guild of Australia (NSW Branch) and Pharmaceutical Society of Australia (NSW Branch) completed a similar process in seeking EOIs to participate in the research. Details were forwarded to the research team with consent. Pharmacies who submitted an expression of interest were assessed to ensure they meet the eligibility criteria for the project.

NSW pharmacies

The contractual arrangements with the NSW Ministry of Health oblige us to offer participation to all New South Wales pharmacies who had consented to the previous trial (UTI) (ACTRN12623000882628). A formal recruitment letter will be sent via email to those 1109 pharmacies who had already previously consented, including the Participant Information Sheet and Consent forms for both Pharmacy and Pharmacist requesting involvement to be signed and returned electronically (Appendix 5-12). Consent will be sought at the pharmacy level from pharmacy owners, and from the individual pharmacists in those pharmacies consenting to participate in the study.

Pharmacies will be sent Participant Information Sheet and Consent forms electronically via DocuSign and have requested individuals to accept the invitation after 10 days. Pharmacies who do not consent in the timeframe will be sent a follow up, 10 days after the initial invitation. For pharmacies/pharmacists who indicate via email they would like further information or clarification, a follow up email and/or phone call will be made by a member of the research team using a standardised script (Appendix 13).

ACT pharmacies

As per the process in NSW, the 5 participating pharmacies in ACT, which were previously randomly selected to ensure a geographic spread of participation across regions, will be sent a formal recruitment letter including the Participant Information Sheet and Consent forms for both Pharmacy and Pharmacist was sent.

The ACT legislation process has been determined by the acting Chief Pharmacist in ACT. Whilst in NSW the Chief Medical Officer signs an Authority for the change, a licence application will need to be made by participating pharmacies. The discretionary licence (available via PDF) would be issued to authorise the 5 pharmacies in the ACT to participate in the trial (Appendix 29). Further details on the licensing can be found on the ACT website: https://www.health.act.gov.au/businesses/medicine-and-poisons-licences-and-permits

4.3.1 Pharmacy and pharmacist eligibility criteria

Pharmacies and pharmacists recruited must meet the eligibility criteria (defined below) to participate in the study, reflecting the criteria set by Authority under Section 10 Poisons and Therapeutic Good Act 1966 Clauses 170 and 171 of the Poisons and Therapeutic Goods Regulation 2208 (please see the NSW Health Authority – Appendix 1- signed by the Chief Medical Officer). All the pharmacies that have expressed an interest to participate will be sent a copy of the Authority. A summary is detailed below:

1. Community pharmacies

- A community pharmacy in NSW or ACT must have a service room, consulting room, or area consistent with the following (as per the Authority):
 - "Ensures the room or area is not to be used as a dispensary, storeroom, staff room or retail area,

- fully enclosed and provides adequate privacy (a divider or curtain in a dispensary, storeroom, staff room or retail area is not acceptable),
- has adequate lighting,
- is maintained at a comfortable ambient temperature,
- has a hand sanitisation facility,
- has ready access to a hand washing facility, and
- has sufficient floor area, clear of equipment and furniture, to accommodate the person receiving the consultation and an accompanying person, and to allow the pharmacist adequate space to manoeuvre."

Pharmacies must have access to MedAdvisor to complete clinical record keeping for the purposes of the clinical trial assessment.

2. Pharmacists

- A community pharmacist holding general registration employed or engaged in an eligible participating pharmacy in NSW and ACT and:
 - who has successfully completed the following training:
 - Australasian College of Pharmacy Continuation of Oral Contraception Course; or
 - Pharmaceutical Society of Australia NSW Contraception Essentials; and
 - Training module(s) that have been approved by the Chief Heath Officer for the purposes of the clinical trial.

A pharmacist is eligible to participate if they hold general registration as a pharmacist with the Australian Health Practitioner Regulation Agency (AHPRA). Pharmacists with provisional registration (intern pharmacists) and pharmacists with conditions on their registration are not eligible to participate in the trial. The pharmacy must have at least one eligible pharmacist who is willing to provide their voluntary consent to participate, for the pharmacy to be eligible, and that there is always a pharmacist available, within reason, to deliver the service during all opening hours of the pharmacy.

4.4 Participant recruitment

A flyer has been developed and approved by the NSW Ministry of Health to inform patients of the service and will be displayed in a prominent location in each participating pharmacy. Female patients will be identified on presentation to the community pharmacy requesting re-supply of their oral contraceptive pill. If meeting the below inclusion criteria, the pharmacist will make an offer to the individual to participate in the study. Patients will be asked for their informed consent to participate in the study via an electronic signature (Appendix 15-18).

4.4.1 Participant consent

All participants will require informed consent. Participants will be provided with two consent forms (one for the study and a second form from Services Australia allowing access to MBS and PBS data). They will be given the option of separate consent. The pharmacist will provide the participant with a location specific QR code for scanning on their mobile phone. This will open a secure webform hosted by the George Institute. The participant will then enter their personal details and be asked to review and tick the boxes. They will then provide a finger signature on a signature panel on the screen and click submit for secure submission to The George Institute. The participant will be sent an SMS or email confirmation message with a validation code which they will provide to the pharmacy.

If participants wish to withdraw from the study once it has started, they can do so at any time without having to give a reason. Withdrawing from the study will not affect their relationship with their employers, professional organisations, care providers or receipt of any care or treatment. Participants wishing to withdraw should notify their pharmacist or one of the research team. Once a participant decides to withdraw from the study, no further information will be collected from them. Their information will be removed from study records and will not be included in the study results.

4.4.2 Participant inclusion criteria

Eligible participants must meet all the following criteria, which are included in the clinical management protocols (Appendix 1 & 2):

- Natal, cis females (capable of pregnancy).
- Aged 18 years of age or over and up to and including aged 35 years.
- Present to community pharmacies in NSW or pharmacies in ACT to obtain a continuing supply of their previously prescribed oral contraceptive pill.
- Patient has been initiated on an oral contraceptive pill by their GP (or other authorised prescribing health care professional) primarily for the indication of contraception and has been stabilised on that pill for 2 years continuously.
- Patient is taking an approved oral contraceptive pill listed in the NSW Health Authority.
- Patient has seen their GP (or other authorised prescribing health care professional) for a review of their oral contraceptive pill in the last 2 years.

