4.5.2 Pharmacy consultation

The pharmacist will undertake a structured consultation with the patient in the community pharmacy guided by an IT program applying one of two clinical management protocols (Combined Oral Contraception and Progestogen-Only Contraception) which encompasses the recommendations from the Australian Therapeutic Guidelines. The clinical management protocol has been subject to co-design between community pharmacists and senior general practitioners with advice from a subject matter expert. This consultation is anticipated to take 10 minutes.

The intervention is provided under the NSW Health Authority allowing participating NSW pharmacists to supply medications as part of the trial. For the ACT, a discretionary licence will be approved for participating pharmacies.

The structured consultation is summarised in Box 1.

BOX 1

- Participant eligibility assessment, in which the pharmacist will assess if the patient meets the inclusion/exclusion criteria to participate in the study.
- Service offering, during which the pharmacist will explain the features of the study and will ask the patient if she/they is willing to participate.
- Electronic provision of the Patient information sheet and informed consent form.
- Patient's clinical assessment. During the assessment the pharmacist will elicit relevant clinical information, including medical conditions, medication history, in line with agreed clinical management protocols. If the patient is a usual patient of the pharmacy, their medication dispensing history may be checked on the computer record, if not the patient medications will be asked. Further information may be obtained from the patients' Electronic Health Record (EHR). Viewing a patients EHR is legally and professionally allowed by pharmacists, with patient consent.
- Clinical measurements of Blood Pressure and BMI will be documented at the initial patient consultation.
- After the clinical assessment, the pharmacist will use one of two clinical management protocols to proceed to resupply.
- Pharmacists may supply a continuation of the oral contraceptive pill (minimum 1 month, and up to 12 months' supply) provided the patient has seen a general practitioner (or other authorised prescribing health care professional in the last 2 years. Pharmacists are not permitted to initiate or change therapy.
- Non-pharmacological management may include:

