4.6.5 Medicare Benefits Schedule (MBS) and Pharmaceutical Benefits Scheme (PBS) data

Participants will be requested at registration to provide consent to access their MBS and PBS data for the evaluation. The Services Australia approved patient and information consent form (Appendix 23) will be used to seek consent. Participants will have the option of authorising Services Australia to provide their claim history for MBS, PBS or both.

As the study will be examining how the use of this service impacts consistency of oral contraception adherence, a 3-year lookback will be requested for PBS data. This will allow analysis of prescribing and dispensing habits over multiple prescribing and refill cycles and to assess discontinuation rates pre and post introduction of the service as a proxy to assessing adherence gaps.

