4.9 Outcomes

Primary outcomes

Primary outcomes will be accessibility and acceptability of the service (based on self-report at 7-day follow up). This will be a composite measure based on patient self-reported data. It includes seven items adapted from existing questionnaires, including a validated questionnaire for perceived service quality in community pharmacies (two items) and studies of pharmacy prescribing for oral contraception, and other medications [1-6]. It will cover the following domains: (a) trust and confidence in health and medical advice provided, (b) convenience, (b) privacy during discussion with pharmacy, and (b) overall satisfaction. Each item is scored on a 7-point Likert scale. Each domain will be equally weighted, and an aggregated score calculated and scaled to a maximum score of 100.

Secondary outcomes

- **On time dispensing rates**: 36 months pre and 12 months post introduction of the intervention (assessed using the proportion of days covered method using PBS data) [40].
- **Primary care utilisation:** MBS records will be used to measure use of general practice services prior up to 36-months pre and 12 months post introduction of the intervention date (MBS data).
- **Safety outcomes**: Adherence rates to Clinical management protocols (assessed by practice change facilitators conducting regular pharmacy monitoring and inspection of data from the patient consultation IT system), hospitalisation for potential pill-related adverse events (e.g., thromboembolic disease) (NSW Health data), rates of STI tests undertaken (MBS pathology data) and adverse events.
- **Implementation outcomes**: Implementation outcomes will also be assessed to examine the fidelity, reach and adoption of the new service, and barriers and facilitators to implementation.

• **Economic outcomes:** Results from the economic analysis will be expressed as (1) net benefit in terms of implementation costs and cost savings arising from more efficient treatment pathways; and (2) cost-consequence results accounting for patient experience measures, relevant safety outcomes and implementation measures. This will be assessed using multiple data sources including MBS records for 36 months pre and 12 months post introduction of the intervention.

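### Entry criteria nearly remove stopping before entry, so the planned pre/post discontinuation contrast would show harm even if the service has no effect

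*Protocol*

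**What the plan says.** Protocol section 4.4.2 requires every participant to meet all the inclusion criteria. Three of them act on the period before entry:

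- She presents "to obtain a continuing supply of their previously prescribed oral contraceptive pill", so she is a current user.
- Her pill was started "primarily for the indication of contraception and has been stabilised on that pill for 2 years continuously".
- She has seen a GP or another authorised prescriber "for a review of their oral contraceptive pill in the last 2 years".

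The before/after outcomes are set elsewhere:

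- Section 4.6.5 asks for a three-year PBS lookback, among other things "to assess discontinuation rates pre and post introduction of the service as a proxy to assessing adherence gaps".
- Section 4.9 defines on-time dispensing over "36 months pre and 12 months post introduction of the intervention (assessed using the proportion of days covered method using PBS data").
- Section 4.9 measures primary care utilisation as "use of general practice services prior up to 36-months pre and 12 months post introduction of the intervention date", and the economic outcomes draw on MBS records over the same windows.

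Section 4.2 describes a cohort design, and no comparison group appears anywhere. Section 4.10.1 adjusts for age, comorbidity count, primary care use in the three years before enrolment, and SEIFA. Nothing in the protocol acknowledges that eligibility conditions 24 of the 36 pre-entry months.

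**The concern.** A single-group before/after contrast has meaning only if it would centre on no change when the service does nothing. Here the entry criteria select on the outcome being compared. A woman who stopped in the last two years is not eligible. A woman who stops in the year after entry is counted. The before period is filtered and the after period is not.

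The listed covariates cannot repair this. They describe differences between women, whereas the bias is within every woman's own timeline. A pre-entry rate that eligibility has set to about zero cannot be recovered by a model.

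At stake is the planned evidence on adherence and, to a smaller degree, on GP use and the savings derived from it. On discontinuation, the likely error is to conclude that pharmacist resupply makes women stop.

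**Working it through.** The protocol gives no stopping rate, PDC value or visit rate, so there is no stated figure to reproduce. Every rate below is an assumption, shown as a range, with no service effect. Time zero is taken as each woman's own entry date.

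**1. Discontinuation.** Under strict application there are no stops in months -24 to 0. If the 12-month stopping risk after entry is a, the constant-hazard rate is -ln(1 - a):

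| a | Post, per 100 person-years | Months -24 to 0 |
|---|---|---|
| 5% | 5.1 | 0 |
| 10% | 10.5 | 0 |
| 20% | 22.3 | 0 |
| 30% | 35.7 | 0 |

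Using all 36 pre-entry months does not rescue the contrast. A monthly simulation of stopping and restarting admitted women with no stop in the last 24 months and at least 18 of them covered. It gave 0.010 stops per woman-year before against 0.114 after (monthly stopping 1%), and 0.021 against 0.218 (monthly stopping 2%). That is roughly a tenfold rise with no effect present.

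**2. PDC.** Assume coverage while on the pill of c = 0.90 both before and after.

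- Post PDC = c × a / h, with h = -ln(1 - a).
- Pre PDC over the conditioned 24 months = c.
- Pre PDC on a fixed 36-month denominator = c × [24 + 12 × (s + (1 - s)/2)] / 36, where s is the share already using at month -36 and the rest start evenly over the next 12 months. This gives 0.825, 0.870 and 0.900 for s = 0.5, 0.8 and 1.0.

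| a | Post | Post minus conditioned 24 months | Post minus fixed 36, s = 0.5 | s = 0.8 | s = 1.0 |
|---|---|---|---|---|---|
| 5% | 0.877 | -0.023 | +0.052 | +0.007 | -0.023 |
| 10% | 0.854 | -0.046 | +0.029 | -0.016 | -0.046 |
| 20% | 0.807 | -0.093 | -0.018 | -0.063 | -0.093 |
| 30% | 0.757 | -0.143 | -0.068 | -0.113 | -0.143 |

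Two biases pull in opposite directions. Selected persistence raises the pre value. Time before a first fill in months -36 to -25, if counted as uncovered, lowers it. In the simulation they nearly cancelled in one case (0.913 before, 0.915 after) and did not in the other (0.887 before, 0.846 after).

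**3. GP visits.** Let visits be Poisson at λ per year, with at least one in the last 24 months.

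- Mean count in the 24 months = 2λ / (1 - exp(-2λ)).
- Adding one unconditioned year, the 36-month rate = (that mean + λ) / 3.

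| λ | Pre rate per year | Post/pre | Spurious fall |
|---|---|---|---|
| 0.5 | 0.694 | 0.72 | 28% (0.19 visits) |
| 1 | 1.104 | 0.91 | 9% (0.10 visits) |
| 2 | 2.025 | 0.99 | 1% |
| 4 | 4.001 | 1.00 | nil |

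With visit rates varying between women (gamma, shape 1), the ratios at mean rates 0.5, 1, 2 and 4 are 0.82, 0.92, 0.97 and 0.99.

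**The case against.** **Continuous use is judged at the consultation**, from dispensing history or by asking the patient (section 4.5.2), not from PBS refill gaps. Some pre-entry gaps will therefore appear in the claims data. This stands, and it is why the pre-entry rate is close to zero rather than certainly zero. The direction survives, because every participant must still be a current user at entry.

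**The PDC denominator is not stated.** Its start date is ordinary analysis-plan detail. This stands too. A reader might infer a 33-point false gain, since a perfect user with exactly 24 months of use scores 24/36 = 67% before and could score 100% after. That is one worst-case woman under a denominator the protocol does not specify. Across a cohort the sign is undetermined.

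**Supply size.** A reader might also infer that post-entry PDC is 100% whatever the use. Section 4.5.2 says "Pharmacists may supply a continuation of the oral contraceptive pill (minimum 1 month, and up to 12 months". A year's supply is thus permitted, not required, and the protocol does not say that it would all appear in PBS data. The point justifies reporting by quantity supplied and no more.

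**GP use covers general practice services in general, not pill reviews alone.** A reader might infer that much of any GP saving is regression to the mean. One guaranteed visit in two years hardly moves a count of several visits a year, and the review may be with a prescriber who is not a GP. This objection largely succeeds.

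**These are secondary outcomes**, and section 4.10.3 already concedes that the cost analysis is limited by the cohort design. That lowers the severity. It does not make the discontinuation contrast interpretable.

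**Conclusion.** The pre/post discontinuation contrast in section 4.6.5 conflicts with the eligibility rule in section 4.4.2 and cannot serve as an effect measure. With no effect it would show about 5 to 36 stops per 100 person-years after entry against about 0 before, for assumed 12-month stopping risks of 5% to 30%. The direction does not depend on the rate assumed.

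PDC is biased by the same selection, by about +0.05 to -0.14 in the scenarios tried. The documents do not settle which sign applies. The GP artefact is minor: 28% at 0.5 visits a year, 9% at 1, about 1% to 3% at 2, and 1% or less at 4 or more.

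It would be too strong to say that eligibility fixes the whole pre-period, since months -36 to -25 are not conditioned by the two-year criteria, or that all three outcomes are distorted to a similar degree. The results rest on time zero being each woman's entry date. Read as a calendar launch date, the conditioned months would partly fall after time zero for later entrants. This should be fixed, but it does not touch the 7-day primary outcome.

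**What to change.** - **Section 4.6.5:** drop pre/post discontinuation as an effect measure. Report 12-month post-entry discontinuation with a confidence interval.
- **Section 4.9, on-time dispensing:** start each woman's denominator at her first observed dispensing, report PDC by quantity supplied, and present the pre/post figures as descriptive, stating that pre-entry persistence is fixed by eligibility. The later start removes uncovered days before the first fill but leaves the -0.023 to -0.143 gap, hence the descriptive label. Cutting the pre window to 12 months would not help, because it would lie wholly inside the conditioned period.
- **Section 4.9, GP use and savings:** add months -36 to -25, which the two-year review criterion does not condition, as a sensitivity baseline. It should not replace the main one, since some women may have started the pill, with visits of their own, in that year.

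These are changes of wording only. They alter no eligibility or clinical rule, and both the three-year PBS lookback and the 36-month MBS window are already planned. The cost is that the adherence evidence becomes descriptive and makes a weaker headline.

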4.4.3 Participant exclusion criteria

- Individuals who are not female.
- Aged <18 years or >35 years.
- Patient has not been initiated on an oral contraceptive pill by their GP (or other authorised prescribing health care professional).
- Patient is not taking an approved oral contraceptive pill listed in the NSW Health Authority.
- Patient has not seen their GP (or other authorised prescribing health care professional) for a review of their oral contraceptive pill in the last 2 years.

See clinical management protocols (Appendix 1 & 2) for further details.

4.5 Intervention description

The intervention is multicomponent.

